15.6 Special and Vulnerable Populations

15.6.1 Inclusion of Women and Minorities

The study is open to anyone regardless of gender or ethnicity; however, we anticipate that the majority of participants will be female based on the demographics of breast cancer. Efforts will be made to extend the accrual to a representative population in term of ethnicity and race.

15.6.2 Exclusion of Pediatric Patients

Pediatric recipients (children <18 years old of age) are excluded from this study because this study is being conducted in the geriatric population.

15.6.3 Exclusion of HIV Positive Individuals

Persons with HIV are not expressly excluded from this study.

15.6.4 Vulnerable Populations

45 CFR §46.111 (a)(3) and 45 CFR §46, Subparts B-D identifies children, prisoners, pregnant women, mentally incapacitated persons, or economically or educationally disadvantaged persons as vulnerable populations.

Adults lacking capacity to consent are not excluded from participation. This study does not pose additional risks for adults lacking capacity than for the general population. In such instances, informed consent will be sought and documented from the prospective participant's legally authorized representative in agreement with institutional policies and local IRB approval.

15.7 Participant Confidentiality

Participant confidentiality is strictly held in trust by the investigators, study staff, and the sponsor(s) and their agents. This confidentiality is extended to cover testing of biological samples in addition to any study information relating to participants.

This research will be conducted in compliance with federal and state requirements relating to protected health information (PHI), including the requirements of the Health Insurance Portability and Accountability Act of 1996 (HIPAA). HIPAA regulations require a signed subject authorization informing the subject of the nature of the PHI to be collected, who will have access to that information and why, who will use or disclose that information, and the rights of a research participant to revoke their authorization for use of their PHI. In the event that a subject revokes authorization to collect or use PHI, the investigator, by regulation, retains the ability to use all information collected prior to the revocation of subject authorization. For subjects that have revoked authorization to collect or use PHI, attempts should be made to obtain permission to collect at least vital status (i.e. that the subject is alive) at the end of their scheduled study period.

Release of research results should preserve the privacy of medical information and must be carried out in accordance with the Department of Health and Human Services Standards for Privacy of Individually Identifiable Health Information, 45 CFR 164.508. When results of this study are reported in medical journals or at meetings, identification of those taking part will not be disclosed and no identifiers will be used.

Medical records of subjects will be securely maintained in the strictest confidence, according to current legal requirements. Data will be entered, analyzed and stored in encrypted, password protected, secure computers that meet all HIPAA requirements. All data capture records, drug accountability records, study reports and communications will identify the patient by initials and the assigned patient number. Source documents provided to coordinating center for the purpose of auditing or monitoring will be de-identified and labeled with the study number, subject ID, and patient initials.

The investigator/institution will permit direct access to source data and documents by sponsor representatives, the FDA, and other applicable regulatory authorities. The access may consist of trial-related monitoring, including remote monitoring, audits, IRB/IEC reviews, and FDA/regulatory authority inspections. The patient's confidentiality will be maintained and will not be made publicly available to the extent permitted by the applicable laws and regulations.

15.8 Conflict of Interest

Any investigator who has a conflict of interest with this study (patent ownership, royalties, or financial gain greater than the minimum allowable by their institution, etc.) must have the conflict reviewed by a properly constituted Conflict of Interest Committee with a Committee-sanctioned conflict management plan that has been reviewed and approved by the study Sponsor (City of Hope) prior to participation in this study. All City of Hope investigators will follow the City of Hope conflict of interest policy.

15.9 Financial Obligations, Compensation, and Reimbursement of Participants

Neither the research participant nor the insurance carrier will be responsible for the research procedures related to this study.

The standard of care drugs or procedures provided during the course of study participation will be the responsibility of the research participant and/or the insurance carrier. The research participant will be responsible for all copayments, deductibles, and other costs of treatment and diagnostic procedures as set forth by the insurance carrier. The research participant and/or the insurance carrier will be billed for the costs of treatment and diagnostic procedures in the same way as if the research participant were not in a research study.

In the event of physical injury to a research participant resulting from research procedures, appropriate medical treatment will be available at City of Hope to the injured research participant. There are no plans for City of Hope to provide financial compensation in the event of physical injury to a research participant.

The research participant will not receive reimbursement or payment for taking part in this study.

15.10 Publication/Data Sharing

Neither the complete nor any part of the results of the study carried out under this protocol, nor any of the information provided by City of Hope for the purposes of performing the study, will be published or passed on to any third party without the written approval of [name] and [name]. Any investigator involved with this study is obligated to provide City of Hope with complete test results and all data derived from the study.

The preparation and submittal for publication of manuscripts containing the study results shall be in accordance with a process determined by mutual written agreement among City of Hope and participating institutions. The publication or presentation of any study results shall comply with all applicable privacy laws, including, but not limited to, the Health Insurance Portability and Accountability Act of 1996.

In accordance with the U.S. Public Law 110-85 (Food and Drug Administration Amendments Act of 2007 or FDAAA), Title VIII, Section 801, this trial will be registered onto ClinicalTrials.gov and results will be reported on ClinicalTrials.gov within 12 months of the estimated or actual completion date of the trial, whichever date is earlier.

APPENDIX A: KARNOFSKY PERFORMANCE STATUS

Karnofsky Performance Scale	
Percent	Description
100	Normal, no complaints, no evidence of disease.
90	Able to carry on normal activity; minor signs or symptoms of disease.
80	Normal activity with effort; some signs or symptoms of disease.
70	Cares for self, unable to carry on normal activity or to do active work.
60	Requires occasional assistance, but is able to care for most of his/her needs.
50	Requires considerable assistance and frequent medical care.
40	Disabled, requires special care and assistance.
30	Severely disabled, hospitalization indicated. Death not imminent.
20	Very sick, hospitalization indicated. Death not imminent.
10	Moribund, fatal processes progressing rapidly.
0	Dead.

APPENDIX B: PROHIBITED MEDICATIONS / MEDICATIONS TO BE USED WITH CAUTION

List of prohibited medications during study drug treatment

Category	Drug Name
Strong CYP3A4/5 inhibitors	Atazanavir/ritonavir, boceprevir, clarithromycin, cobicistat, conivaptan, danoprevir/ritonavir, darunavir/ritonavir, elvitegravir/ritonavir, grapefruit juice, idelalisib, indinavir, indinavir/ritonavir, itraconazole, ketoconazole, lopinavir/ritonavir, mibepradil, nefazodone, neflunavir, ombitasvir/paritaprevir/dasabuvir/ritonavir (VIEKIRA PAK), posaconazole, ritonavir, saquinavir/ritonavir, telaprevir, telithromycin, tipranavir/ritonavir, troleandomycin/voriconazole
Strong CYP3A4/5 inducers	carbamazepine ³ , enzalutamide, lumacaftor, mitotane, phenobarbital, phenytoin ³ , rifabutin, rifampin (rifampicin) ³ , St. John's wort (hypericum perforatum) ^{2,3}
CYP3A4/5 substrates with NTI¹	Alfentanil, astemizole, cisapride, cyclosporine, diergotamine (dihydroergotamine), ergotamine, fentanyl, pimozide, quinidine, sirolimus, tacrolimus
Medications with a known risk for QT prolongation⁴	Amiodarone, anagrelide, arsenic trioxide, astemizole, azithromycin, chloroquine, chlorpromazine, cilostazol, ciprofloxacin, cisapride, citalopram, clarithromycin, disopyramide, dofetilide, domperidone, donepezil, dronedarone, droperidol, erythromycin, escitalopram, flecainide, fluconazole, gatifloxacine, grepafloxacin, halofantrine, haloperidol, ibutilide, levofloxacin, levomepromazine, levosulpiride, methadone, moxifloxacin, ondansetron, oxaliplatin, papaverine HCl (intra-coronary), pentamidine, pimozide, procainamide, propofol, quinidine, roxithromycin, sevoflurane, sotalol, sulpiride, sultopride, terlipressin, terodilane, thioridazine, vandetanib
Herbal preparations/ medications	Herbal preparations/medications known as strong inducers or inhibitors of CYP3A4/5 or those with a known risk of QT prolongation are prohibited throughout the study. These herbal medications include, but are not limited to: St. John's wort, Kava, ephedra (ma huang), gingko biloba, dehydroepiandrosterone (DHEA), yohimbe, saw palmetto, and ginseng. Patients should stop using these herbal medications 7 days prior to first dose of study drug.
Other investigational and antineoplastic therapies	Other investigational therapies must not be used while the patient is on the study. Anticancer therapy (chemotherapy, all SERMS (including raloxifene), biologic or radiation therapy, and surgery) other than the study treatments must not be given to patients while the patient is on the study medication. If such agents are required for a patient then the patient must be discontinued study drug.

¹ NTI = narrow therapeutic index drugs whose exposure-response indicates that increases in their exposure levels by the concomitant use of potent inhibitors may lead to serious safety concerns (e.g., Torsades de Pointes) or drugs which have <2-fold difference in the minimum toxic concentrations and minimum effective concentrations in the blood.

² Herbal product

³ P-gp inducer

⁴ The list provided is as of January 2018. Check <https://www.crediblemeds.org/healthcare-providers/drug-list> for the most updated list.

As far as possible, avoid co-administration of QT prolonging drugs or any other drugs with the potential to increase the risk of drug-related QT prolongation (e.g., via a potential DDI that increases the exposure of ribociclib or the exposure of the QT prolonging drug). A definitive list of drugs with a known risk, possible risk, or conditional risk of QT prolongation and/or Torsades de Pointes (TdP) is available online at qtdrugs.org. Source: Novartis PK Sciences Memorandum: Drug-Drug Interactions (DDI) and Co-medication Considerations for Novartis Clinical Trials (January 2018), which is compiled from Indiana University "Clinically Relevant" Flockhart Table™, University of Washington Drug Interaction Database, and FDA Drug Development and Drug Interactions: Table of Substrates, Inhibitors and Inducers.

List of medications to be used with caution during study drug treatment

Category	Drug Name
Moderate CYP3A4/5 inhibitors	Aprepitant, amprenavir, asafoetida resin (Ferula asafoetida) cimetidine, crizotinib, diltiazem, faldaprevir, imatinib, isavuconazole, netupitant, nilotinib, tofisopam, Schisandra sphenanthera (nan wu wei zi), verapamil
Moderate CYP3A4/5 inducers	Bosentan, dabrafenib, efavirenz, etravirine, genistein, lopinavir ⁵ , modafinil, naftcilin, telotristat
Sensitive CYP3A4/5 substrates¹	Alpha-dihydroergocryptine, aprepitant, atorvastatin, avanafil, bosutinib, brotizolam, budesonide, buspirone, cobimetinib, darifenacin, dasatinib, ebastine, eletriptan, eplerenone, everolimus, felodipine, fluticasone, grazoprevir, ibrutinib, isavuconazole, ivabradine, ivacaftor, , levomethadyl (LAAM), lomitapide, lovastatin, lumefantrine, lurasidone, maraviroc, midazolam, midostaurin, naloxegol, neratinib, nisoldipine, perospirone, quetiapine, ridaforolimus, sildenafil, simeprevir, simvastatin, ticagrelor, tilidine, tolvaptan, triazolam, ulipristal, vardenafil, venetoclax, viceriviroc, voclosporin
BSEP inhibitors	Alectinib, atorvastatin, bromocriptine, candesartan, clobetasol, clofazimine, dabigatran, dipyridamole, glyburide, grazoprevir, ledipasvir, mifepristone, pioglitazone, reserpine, rifamycin, simeprevir, telmisartan, timcodar, troglitazone,

	valinomycin, velpatasvir
Medications that carry a possible risk for QT prolongation²	Alfuzosin, apomorphine, aripiprazole, artenimol+piperaquine , asenapine, atomoxetine, bedaquiline, bendamustine, bortezomib, bosutinib, buprenorphine, cabozantinib, capecitabine, ceritinib, clomipramine, crizotinib, clozapine, cyamemazine (cyamepromazine), dabrafenib, dasatinib, degarilix, delamanid, desipramine, dexmedetomidine, dolasetron, efavirenz, eliglustat, epirubicin, eribulin mesylate, ezogabine(retigabine), famotidine, felbamate, fingolimod, flupentixol, gemifloxacin, granisetron, hydrocodone-ER, iloperidone, imipramine (melipramine), isradipine, ketanserin, lapatinib, lenvatinib, leuprolide, lithium, melperone, midostaurin, mifepristone, mirabegron, mirtazapine, moexipril/HCTZ, necitumumab, nicardipine, nilotinib, norfloxacin, nortriptyline, nusinersen, ofloxacin, osimertinib, oxytocin, paliperidone, palonosetron, panabinstat, pasireotide, pazopanib, perflutren lipid microspheres, perphenazine, pilsicainide, pimavanserin, pipamperone, promethazine, prothipendyl, rilpivirine, risperidone, romidepsin, sertindole, sorafenib, sunitinib, tamoxifen, tipiracil/trifluridine, tizanidine, tolterodine, toremifene, trimipramine, tropisetron, vardenafil, vemurafenib, venlafaxine, vorinostat, ziprasidone
MATE1/2 substrates³	Acyclovir, cephalexin, cimetidine, fexofenadine, ganciclovir, glycopyrronium, metformin, pindolol, plisicainide, ranitidine, topotecan, varenicline
OCT1/2 substrates⁴	Amantadine, 6-beta-hydroxycortisol, carboplatin, cisplatin, cephalexin, cephadrine, ipratropium, lamivudine, linagliptin, metformin, oxyplatin, oxybutynin, phenformin, picoplatin, pilsicainide, pindolol, ranitidine, sorafenib, tropisetron, trospium, umeclidinium,, and zidovudine
BCRP substrates	Daunorubicin, dolutegravir, doxorubicin, hematoporphyrin, imatinib, methotrexate, mitoxantrone, pitavastatin, rosuvastatin, irinotecan, ethinyl estradiol, simvastatin, sulfasalazine, sofosbuvir, tenofovir, topotecan, venetoclax

¹ Sensitive substrates: Drugs whose plasma AUC values have been shown to increase 5-fold or higher when co-administered with a potent inhibitor.

² The list provided is as of January 2018. Check <https://www.crediblemeds.org/healthcare-providers/drug-list> for the most updated list.

³ MATE1 and MATE2 share considerable substrate specificity.

⁴ OCT1 and OCT2 share considerable substrate specificity.

⁵ Lopinavir is prohibited when combined with ritonavir (see Table 14-1)

Source: Novartis PK Sciences Memorandum: Drug-Drug Interactions (DDI) and Co-medication Considerations for Novartis Clinical Trials (January 2018), which is compiled from Indiana University “Clinically Relevant” Flockhart Table™, University of Washington Drug Interaction Database, and FDA Drug Development and Drug Interactions: Table of Substrates, Inhibitors and Inducers.

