5.4. Duration of Protocol Therapy - Criteria for Ending Protocol Therapy

Participants will receive protocol therapy until one of the below criteria are met:

- Disease progression
- Participant is deemed intolerant to ribociclib because of toxicity, despite dose modification/ delay
- General or specific changes in the patient's condition which render the patient unacceptable for further treatment in the judgment of the investigator
- Withdrawal of consent for further protocol therapy by the participant (See [Section 17.5](#))

Once participants meet criteria for removal from protocol therapy, the participant should then proceed to End of Treatment and 30-Day-Post Last-Dose visits.

Documentation of the reason for discontinuing protocol therapy and the date effective should be made in the medical record and appropriate eCRF. **The COH DCC should be promptly notified of the change in participant status.**

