5.5. Long-Term Follow-Up

All participants whose disease had not progressed at the time of end of protocol therapy will undergo **medical chart review for disease progression/response** information until disease progression or the initiation of a new therapy. Medical chart review should occur at least twice annually or as requested by the lead study team.

All participants will be followed for **survival information** by the site and/or by the lead study team designee. If performed by the lead study team, the following information will need to be transferred to the designee in a secure manner: the participant's first and last name, middle initial, social security number, date of birth, and gender. Methods for capturing survival status may include the Social Security Death Index and the National Death Index. Survival analysis will be conducted at least annually or as requested by the lead study team.

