5.7.1. Prohibited until end of protocol therapy

End of protocol therapy is when treatment with ribociclib will no longer continue.

- No other investigational therapy should be given to participants
- No anticancer agents other than the study medications administered as part of this study protocol should be given to participants. If such agents are required for a participant then the participant must first be withdrawn from the study.
- Co-medication that may interfere with study results; e.g. immuno-suppressive agents other than corticosteroids, such as systemic cyclosporine and tacrolimus are prohibited during the treatment phase of the study, unless discussed with principal investigator felt to be of low clinical risk to the participant.
- Use of herbal medications may have unknown interactions with the metabolism of the study agents, and therefore are prohibited from use during the treatment phase of the trial.
- Strong CYP3A inhibitors/inducers including St. John's Wort and Grapefruit. Refer to [Appendix B](#) for an extensive list.
- Drugs known to cause QT interval prolongation. Refer to [Appendix B](#) for an extensive list.
- Hormone replacement therapy, topical estrogens (including any intra-vaginal preparations), megestrol acetate and selective estrogen-receptor modulators (eg, raloxifene).

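### Appendix B, Section 5.7.1 and Section 5.4 differ on whether needing radiotherapy or surgery without progression ends therapy, and on whether the patient then stops drug or leaves the study

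*Combined protocol and SAP*

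**What the plan says.** Three places bear on anticancer treatment given during protocol therapy.

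- **Appendix B, row on other investigational and antineoplastic therapies.** The barred treatments include "biologic or radiation therapy, and surgery) other than the study treatments must not be given to patients" while they are on study medication. The consequence follows: "If such agents are required for a patient then the patient must be discontinued study drug".
- **Section 5.7.1.** "No anticancer agents other than the study medications administered as part of this study protocol should be given to participants". The consequence is: "If such agents are required for a participant then the participant must first be withdrawn from the study". Radiotherapy and surgery are not named. The section sends the reader to Appendix B for the CYP3A and QT lists only.
- **Section 5.4.** "Participants will receive protocol therapy until one of the below criteria are met". The four criteria are progression, intolerance of ribociclib, withdrawal of consent, and "General or specific changes in the patient's condition which render the patient unacceptable for further treatment in the judgment of the investigator". Footnote b of the study calendar points to this section as the fuller list for ending treatment and does not mention Appendix B.

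Follow-up and response are covered elsewhere. Under Section 5.5, patients who end therapy without progression have chart review at least twice a year "until disease progression or the initiation of a new therapy", and all patients are followed for survival. Section 5.6 lists participant withdrawal among the events that may end study participation. Section 12.4.3 takes best response from the start of treatment to progression on a single timepoint. Section 12 has no rule for a target lesion treated locally on study.

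**The concern.** The need is foreseeable. All patients have metastatic disease, the synopsis admits bone-only disease, and exclusion 12 already sets a minimum interval between radiotherapy or major surgery and the first dose. The protocol thus considers these treatments at entry, but its body text has no rule for them during treatment.

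A coordinator who follows the calendar to Section 5.4, and its concomitant-medication footnote to Section 5.7.1, is not led to the Appendix B row on radiotherapy. Depending on which text is applied, a non-progressing patient might continue ribociclib, stop it and enter Section 5.5 follow-up, or leave the study. That choice affects the number of cycles completed (summarised under Section 13.4), how progression is ascertained for PFS, and possibly whether survival is followed. Separately, shrinkage caused by local treatment could be credited to the drug combination in the objective response rate.

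**Working it through.** The plan gives no figure on this point, so the check is a comparison of texts.

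**Step 1. The three places side by side**

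| Place | What it bars | Radiotherapy or surgery named? | Consequence |
|---|---|---|---|
| Appendix B | Anticancer therapy other than study treatment | Yes, both | Study drug stops (mandatory) |
| Section 5.7.1 | Anticancer agents other than study medication | No | Participant leaves the study (mandatory) |
| Section 5.4 | Not a ban; lists criteria for ending therapy | No | Therapy ends only if a listed criterion applies; the nearest is discretionary |

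**Step 2. A patient without progression who needs radiotherapy or surgery.** Appendix B bars the treatment. Its stop sentence speaks of agents but follows a list that contains radiation and surgery, so it most naturally covers them. Section 5.7.1 either does not reach the case (agents meaning drugs) or requires withdrawal from the study (agents read widely). Section 5.4 ends therapy only if the investigator judges the patient unacceptable for further treatment. Neither reading of Section 5.7.1 brings all three places to the same result.

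**Step 3. A patient without progression who needs another anticancer drug.** Appendix B and Section 5.7.1 both cover this case, whatever *agents* means. One stops study drug and the other removes the participant from the study. Section 5.7.1 is also headed as applying until the end of protocol therapy, which it defines as the point when ribociclib no longer continues. Its ban therefore lapses once drug stops, yet its stated consequence goes further.

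**Step 4. What the two consequences mean for follow-up.**
- On treatment, CT is done before Cycle 3 and then every 3 cycles: 3 × 28 = 84 days, or 12 weeks.
- After stopping drug, Section 5.5 gives chart review at least twice a year, or as the lead team requests, plus survival follow-up. It does not say whether radiotherapy counts as the new therapy that ends chart review.
- After leaving the study, Section 5.6 allows participation to end. Section 15.5 describes three levels of participant withdrawal, from stopping treatment only to stopping all data collection. Section 5.7.1 does not say which level it means.

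**Step 5. Response.** PR needs at least a 30% fall in the sum of target-lesion diameters, with at most five targets (Sections 12.2 and 12.4.1). For lesions of equal size, one that disappears while the others are unchanged lowers the sum by 1/2 = 50% of two, 1/3 = 33% of three, 1/4 = 25% of four or 1/5 = 20% of five. One locally treated lesion could thus produce a PR unaided with three or fewer equal targets, but not with four or five. No confirmatory scan is required, and nothing in Section 12 excludes the treated lesion. Calendar footnote q collects prescription and over-the-counter medicines, and the calendar has no entry for on-study radiotherapy or surgery.

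**The case against.** The strongest reply is that this is incomplete cross-referencing and not a conflict of rules. Appendix B belongs to the same protocol, binds every site and is the more specific text. It uses the word agents for a list that includes radiation and surgery, so Section 5.7.1 can be read the same way. The investigator-judgment criterion in Section 5.4 lets an investigator stop therapy as Appendix B requires. Sections 5.4 and 5.7.1 are silent on radiotherapy; they do not permit it. The endpoints touched are descriptive secondary ones in a single-arm study.

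Most of this is right, and it rules out several stronger readings that a reader might infer:

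- *That Section 5.4 is a closed list which keeps the patient on ribociclib.* Its third criterion is open.
- *That one site will keep such a patient on and another will take the patient off.* The documents show only that this is possible.
- *That the effect can be counted,* for example 5% to 15% of 40, or 2 to 6 patients, each moving a rate by 1/40 = 2.5 points. The documents give no rate. Patients needing local treatment are not the same as patients handled differently. The response denominator is the measurable, re-evaluated subset defined in Section 12.1, not a fixed 40. A patient lost to PFS follow-up is a censored time, not a shift of 1/40.
- *That an irradiated painful bone lesion in bone-only disease becomes a false response.* The synopsis sets bone-only disease as the alternative to measurable disease, and Section 12.1 limits response evaluation to patients with measurable disease.

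Three things survive. A discretionary criterion does not match a mandatory one. Reading *agents* widely makes the consequences clash instead of agree. The response gap in Step 5 remains however the prohibition is read.

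**Conclusion.** The texts are inconsistent on two counts: whether needing radiotherapy or surgery without progression ends therapy, and whether the consequence is stopping drug or leaving the study. The second is the plainer conflict, because for other anticancer drugs it depends on no reading of *agents*. The first assumes that the Appendix B stop sentence is meant to reach radiation and surgery. If it is not, Appendix B bars them without stating a consequence, and that also needs correcting.

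No numerical size can be given. The effects fall on time on treatment, progression and possibly survival follow-up, and objective response. The definition of the primary endpoint, grade 2 or higher toxicity attributed to ribociclib, is unaffected. The point should be corrected, but it does not threaten the trial's main result.

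**What to change.** 1. Reconcile Section 5.4, Section 5.7.1 and the Appendix B row so that they state one rule for radiotherapy and surgery during protocol therapy, and one consequence for any barred anticancer treatment. The clinical rule is the sponsor's to decide; none is proposed here.
2. State whether progression and survival follow-up under Section 5.5 continues for these patients.
3. Record the date and site of any radiotherapy or local surgery before progression.
4. State in Section 12.4 that shrinkage of a locally treated target lesion does not count toward CR or PR from the date of that treatment.

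The cost is a few sentences, one CRF field for date and site, and a possibly slightly lower objective response rate.
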